1.16 Metformin and Long COVID

Although clinical trials using metformin in participants with acute COVID-19 have not demonstrated efficacy in reducing clinically relevant events or symptoms, data suggest that prolonged use and/or prolonged follow-up of participants taking metformin may result in a lower incidence of dyspnea, fatigue, tiredness, and nonspecific neurological symptoms.

Bramante et al. reported the results of a 10-month follow-up in their original clinical trial²²¹. The authors obtained data from 1,125 participants in a pre- follow-up specified as a secondary analysis of the original study, including 564 participants exposed to metformin and 561 participants not exposed to metformin. Assessments were conducted remotely via a questionnaire sent by email. Among participants randomized to the metformin arm, 6.2% (95% CI 4.2–8.2%) reported worsening symptoms after developing COVID-19, compared with 10.6% (95% CI 8.0–13.1%). The reduction in the risk of developing Long COVID in this population was estimated at 58% compared to the placebo group.

Cumulative incidence of “Long COVID,” post-acute sequelae of SARS-CoV-2 infection (PASC), diagnosed by a physician more than 10 months after randomization. Adapted from ref 206.

Although it shows a reduction of over 50% in the incidence rate of Long COVID compared to placebo, the clinical trial by Bramante et al. must be interpreted with caution. This data was collected remotely, without a standardized definition of Long COVID, as this diagnosis was reported by the attending physician at various clinics across the United States. Furthermore, the information was collected remotely, and data were missing for more than 6% of the original sample. The information was based on a proprietary scale, and participants were subsequently exposed to more than one potentially therapeutic agent.

These limitations point to the need to seek evidence regarding a possible link between metformin and long COVID.

2 STUDY OBJECTIVES

The objective of this study is to evaluate the efficacy, safety, and benefits of using fluvoxamine and metformin in participants with a clinical diagnosis of long COVID who are being monitored at Primary Health Care Units in Brazil. The research subject's participation in the protocol lasts up to 90 days, with an initial phase of up to 60 days considered the treatment phase and the period of up to 90 days considered the follow-up period for the study and verification of the study's clinical results.

2.1 Objectives/Primary Outcome

The primary objective is to compare the use of Fluvoxamine and Metformin with placebo for the mean score on the Fatigue Severity Scale (FSS) on day 60 after randomization by at least 1 point.

2.2 Secondary objectives/ outcomes

The secondary objectives are:

- To compare fluvoxamine and metformin with placebo for the mean FFS score 30 days after randomization.
- To compare fluvoxamine and metformin with placebo for the mean FSS score 60 days after randomization.
- To compare fluvoxamine and metformin with placebo regarding the mean difference in the change in health-related quality of life (HRQL) as measured by the EQ-5D-5L at 60 days from randomization.
- Compare fluvoxamine and metformin with placebo for the odds ratio of all-cause mortality at 60 days after randomization.
- Compare fluvoxamine plus metformin with placebo for the odds ratio of unexpected hospitalization from all causes at 60 days.
- To assess the safety of fluvoxamine and metformin in this population of participants.
- To evaluate the mid-term post-study effects (90 and 180 days) of the investigational medicinal products on the chronic fatigue scale (FSS scale) and quality of life (EQ-5D-5L).

3 RESEARCH PLAN

3.1 Study Design

[figure not shown]
This is a prospective, multicenter, adaptive, double-blind, randomized, placebo-controlled study to evaluate the effect of different therapies on reducing fatigue levels in participants with long-standing chronic fatigue syndrome. The treatment groups will be fluvoxamine, metformin, and the corresponding placebo.

Participants will be randomized to one of the study arms using an independent, automated, iterative centralized randomization system (IVRS or IWRS). The protocol includes an adaptive phase to accommodate any pre-specified modification needs.

The protocol is designed to enroll 1,500 participants, with 500 participants in each study arm in an equal randomization ratio (e.g., 1:1:1). The protocol includes three planned interim analyses to occur at 25%, 50%, and 75% of the total number of participants. These interim analyses will allow for potential termination based on superiority, in the event of clear evidence of efficacy, or termination due to futility, in the event of insufficient evidence of efficacy. The decision thresholds for efficacy and futility are calibrated using statistical simulations to ensure control of the Type I error rate at 0.025 in each of the pairwise comparisons between the experimental treatment arm and the control. These interim evaluations will be conducted by the Data Safety Committee, which will be supported by statisticians, and decisions will be communicated to the Steering Committee for appropriate regulatory action, when applicable. Any decision to discontinue treatment will be subject to immediate notification to regulatory authorities and the Ministry of Health, in accordance with current regulations.

Fluxograma da Pesquisa

Braços Fluvoxamina, Metformina e Placebo

1. Tratamento: Fluvoxamina, Metformina e placebo em grupos paralelos pelo período planejado. Posologia das medicações varia conforme a alocação do paciente em um braço do estudo (Para cada braço há o correspondente placebo, na mesma formulação e posologia. Medicações serão interrompidas a qualquer momento se houver evidência de reação adversa, a critério do sujeito da pesquisa ou por recomendação do DSMB (eficácia, futilidade ou segurança do participante).
2. Triagem e Randomização devem ser realizadas na mesma visita. Assegurar que o paciente seja randomizado por ocasião do atendimento.
3. As visitas subsequentes: D₃₀ a D₉₀, D₉₀ serão realizadas através de contato telefônico, telemedicina ou aplicativos de mídias sociais, entretanto com possibilidade de visitas presenciais, caso necessário. Em qualquer momento visitas extras de segurança poderão ser realizadas, inclusive presenciais. A visita D₉₀ é considerada a visita de desfecho para a pesquisa. A visita D₉₀ é considerada visita pós-estudo, para acompanhamento de eventuais complicações tardias/ persistência de sintomas relacionados ao COVID-19 e também para avaliação eventual de reações adversas tardias aos medicamentos da pesquisa. Esta será realizada através de contato telefônico. Não há previsão de visitas presenciais regulares nesta pesquisa, entretanto recomendamos que a visita D₉₀ seja preferencialmente realizada presencialmente.
4. Visitas adicionais poderão ser realizadas seja por sugestão da equipe de pesquisa seja por solicitação do participante.

Research flowchart

3.2 Rationale for the study design

The COVID-19 pandemic has not only emphasized the importance of randomized clinical trials following proper methodology and adopting consistent practices in the planning, conduct, and analysis of the data obtained, but above all has demonstrated the need for the development and conduct of large-scale clinical trials, structured according to a master protocol, in a coordinated manner and through global collaboration²²². Therapeutic research for acute COVID-19 has resulted in futile efforts by most research groups, as, although thousands of trial records have emerged, most of them lack a consistent methodology, exhibit significant biases, and contain major flaws in their conduct and in the interpretation of results.

Based on this perspective for long COVID-19, we proposed an adaptive platform study project, similar to the TOGETHER study conducted by our research group in several municipalities in the state of Minas Gerais and approved by this committee. Protocols with an adaptive design, through the “perpetual” study of more than one therapeutic intervention, can be evaluated and discarded (via a robust statistical analysis and evaluation plan) if they show no evidence of benefit²²³. These studies create opportunities to generate more efficient knowledge, which can be

incorporated into routine clinical practice and promote continuous improvements. With their common platform and infrastructure, efficient use of control arms, and ability to expedite the launch of new study interventions, adaptive clinical trials can offer numerous advantages in identifying effective drugs and devices to combat COVID-19 and in comparative efficacy scenarios—quickly and efficiently, without compromising the quality of a randomized clinical trial^{224,225(,) 226}.

3.3 Rationale for the dose/regimen, route of administration, and duration of treatment

3.3.1 Fluvoxamine

Fluvoxamine is an SSRI antidepressant with anti-inflammatory activity due to its 5-HT_{1A} agonist effect. In the TOGETHER clinical trial, we administered a dose of 100 mg orally every 12 hours for 10 consecutive days in patients with acute influenza-like illness. We used this dose in two arms: initially as monotherapy¹⁸⁶ and subsequently in combination with budesonide¹⁸⁷, with tolerability and safety comparable to the placebo group. A dose of 50 mg administered orally every 12 hours was tested in some clinical trials but did not demonstrate efficacy, suggesting that a 50 mg dose every 12 hours is insufficient to elicit anti-inflammatory effects via 5-HT_{1A} receptors^{220,221}.

The 60-day period is necessary because evidence suggests that Long COVID is related to a severe and persistent disruption of the immune-inflammatory balance, involving key pathways that require at least 3–4 weeks to restore equilibrium. Furthermore, clinical case reports using these drugs for a short period of time have failed to demonstrate benefits.

3.3.2 Metformin

Participants randomized to the metformin arm will receive a dose of 500 mg twice daily for a period of 60 days. We chose to modify the metformin dose in the clinical trial for two reasons: (1) To align with the international literature, which has used a 500 mg dose every 12 hours in clinical trials to evaluate Long COVID, and (2) following a blinded analysis of the first 100 recruited participants, where we identified a dropout rate due to mild adverse effects (diarrhea, abdominal pain, nausea) in 9% of participants (common symptoms associated with the use of higher doses of metformin). In particular, the study by Bramante et al. observed a lower incidence of Long COVID in participants in the COVID OUT study's Metformin Arm, where the dose used was 500 mg every 12 hours²¹⁸. There is evidence that doses exceeding 750 mg twice daily do not result in a better inflammatory profile. The metformin dose was selected based on previous observational evidence of a dose response at

1,000 mg per day and is consistent with our previous TOGETHER study of metformin vs. placebo²¹⁹ and a similar study²²⁰. We chose to use the extended-release formulation because it causes fewer gastrointestinal side effects and has more consistent and stable bioavailability, which is an advantage in providing a uniform serum dose. Since metformin is well tolerated over long periods²²⁷, to observe its potential effect in participants with prolonged COVID-19, we chose a 60-day duration, considering the pathogenesis of the immuno-inflammatory changes present in Long COVID, which often require a therapeutic action period of 3–4 weeks for the expected effects, this being a possible explanation for the futility of using metformin in acute forms of COVID-19.

3.5 Rationale for the trial

Currently, there are no approved therapies for the treatment of Long COVID. Given the complex disease process, high work disability, and persistent symptoms associated with the condition, evidence is needed to support the safety and efficacy of treatments.

Few randomized studies of outpatient treatment for COVID-19 have followed participants for a long period after acute treatment to assess the effect of early treatments on the incidence of post-COVID-19 conditions. Although the mechanism of action has not been fully elucidated, metformin is known to alter glucose metabolism and is being investigated as an antiviral agent, demonstrating in vitro and in vivo activity against SARS-CoV-2. Recent studies suggest that metformin may also serve as a therapeutic option for participants with long COVID-19²²¹.

4 RESEARCH PLAN

4.1 Study Design

The study consists of an in-person screening and randomization visit, which will occur simultaneously, and visits conducted via in-person visits, telephone contact, and social media applications using video conferencing. The following visit schedule will be implemented for the metformin and corresponding placebo arms (adjusted for treatment days according to the intervention arms):

- V1 (Day 1) - Screening, Baseline, Randomization (Start of treatment phase)
- V2 (Day 7) - Follow-up Visit / Tolerance to Investigational Medicinal Products
- V3 (Day 30) - Follow-up visit
- V4 (Day 60) - Follow-up visit (in-person visit recommended)
- V5 (Day 90) - Follow-up visit after completion of the investigational product
- V6 (Day 180) - Follow-up visit after completion of the investigational product

The D90 and D180 visits are considered post-study visits. The objective of these visits is to evaluate late effects of the investigational medical products and the persistence of any therapeutic effect observed during the treatment phase. This phase is an open-label, post-study phase.

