6. STUDY TREATMENTS

6.1 *Treatment blinding*

To minimize the potential for bias during the treatment phase, treatment randomization information will be kept confidential by a non-blinded biostatistician and will not be disclosed to third parties until the study database is finalized for statistical analysis upon completion of recruitment and follow-up of the last scheduled patient. The study is blinded, and neither the patient nor the investigator, the research team, nor existing committees will have access to the contents of the vials, which are produced sealed and hermetically closed. Similarly, the sponsor and the designated person will not have access to the randomization data. Treatment vials will be distributed using codes maintained by an unblinded biostatistician not involved in the research. The Data Monitoring Committee (DMC) and the drug safety team will not have access to participant allocation during the

interim assessments planned in the study, except in foreseeable situations (decision to discontinue any arm of the study, whether due to efficacy or futility, termination of the study, or for reasons of overall participant safety).

The clinical trial supply management team will have access to general information on investigational products at the site level for the management of packaging and distribution activities, as well as for the supervision of investigational product inventory levels in drug warehouses and at study sites, but will not have access to the allocation codes for these products.

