12.2 Randomization

Participants will be randomly assigned to one of the study arms in an equal allocation (e.g., 1:1:1). Stratified permuted block randomization will be used for this study. Randomization will be stratified by participating primary care facility with varying block sizes of participants. We will use a computer-generated interactive voice/web response system to implement randomization. For each active drug arm, there will be a placebo (or active control) arm, including for the different formulations and dosages in the study.

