12.11 Summary table of analyses from the website

Result	Hypothesis	Outcome Measure	Statistical analysis method
Primary Mean score measured by the fatigue severity scale on day 60 after randomization	Drug treatment will be better than placebo	Fatigue Severity Scale	Bayesian Normal-Normal analysis
Secondary Mean score measured by the fatigue severity scale on day 30 after randomization	Drug treatment will be better than placebo	Fatigue Severity Scale	Bayesian Normal-Normal Analysis
Mean score measured by the fatigue severity scale on day 90 after randomization	Drug treatment will be better than placebo	Fatigue Severity Scale	Bayesian Normal-Normal Analysis
Health-related quality of life on day 60 after randomization	Drug treatment will be better than placebo		Bayesian Normal-Normal Analysis
All-cause mortality by day 60 after randomization	Treatment will prevent overall mortality	Measuring deaths in the groups	Logistic regression
Time to all-cause mortality up to day 60 after randomization	The treatment will prevent overall mortality	Interval in days between randomization and mortality	Cox regression
Unexpected hospitalization from any cause by day 60 after randomization	The treatment will prevent hospitalization	Measurement of deaths in the groups	Logistic regression
Unexpected hospitalization for any cause up to day 60 after randomization	The treatment will prevent hospitalization	Interval in days between randomization and mortality	Cox regression
Safety of the IP	The drugs are safe in participants with long COVID	Measurement of adverse events in treatment groups	Descriptive analysis
3) Subgroup analysis: i) Age (young vs. elderly) (ii) Sex (male vs. female) female)	Older adults are at higher risk of complications Men are at higher risk	Risk assessment	Regression methods with appropriate interaction terms.

iv) Vaccination status	Unvaccinated individuals are at higher risk		
v) Obesity	Obesity carries a higher risk		
vi) Diabetes	Diabetes carries a higher risk		
vii) Hypertension			
viii) Cardiovascular disease	People with high blood pressure are at higher risk		
ix) Chronic lung disease	Lung disease carries a higher risk		
4) Sensitivity analysis	The results remain robust	Primary and key secondary outcomes (fatigue score at day 30 and day 60)	

IMPORTANT NOTES:
 
 In all analyses, results will be expressed as estimated effects with corresponding 95% uncertainty estimates 			

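### Section 4.1 calls the day 90/180 follow-up open-label, which contradicts the blinding rule in section 6.1 and exposes self-reported durability outcomes to bias if applied as written

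*Protocol*

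**What the plan says.** Section 4.1 (Study Design) places the day 90 and day 180 visits in a post-study period whose purpose is to "evaluate late effects of the investigational medical products and the persistence of any therapeutic effect observed during the treatment phase". It then adds: "This phase is an open-label, post-study phase".

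Section 6.1 (Treatment blinding) withholds the randomization information "until the study database is finalized for statistical analysis upon completion of recruitment and follow-up of the last scheduled patient". It also states that "neither the patient nor the investigator, the research team, nor existing committees will have access to the contents of the vials".

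Outcomes measured in that period:

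- The synopsis lists FSS at day 90 as secondary objective 2 and secondary outcome 2.
- Section 12.11 lists it among the secondary results ("Mean score measured by the fatigue severity scale on day 90 after randomization"), with a Bayesian normal-normal analysis and the hypothesis that drug is better than placebo.
- The synopsis and section 2.2 both list FSS and EQ-5D-5L at 90 and 180 days as an objective.
- Section 8.3 schedules both questionnaires at both visits. Section 9.4 says that participants complete them.

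**The concern.** A site cannot follow both statements. One tells it that follow-up after day 60 is open; the other tells it that nobody at the site, nor the participant, learns the allocation before the database is final.

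The affected data are efficacy data. The visits exist to ask whether an effect lasts after treatment stops, and the answer comes from self-rated fatigue and quality of life. A participant who knows that the tablets were placebo, or were active, may rate fatigue differently for that reason alone. The comparison would then mix persistence of effect with expectation. Once a participant has been told, the blind cannot be restored for that person's later ratings, so the text should be settled before anyone acts on it.

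**Working it through.** The protocol states no figure on this point, so there is none to reproduce. The check is a comparison of texts, followed by an illustration.

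**1. Do the two statements conflict?**

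| Question | Section 4.1 | Section 6.1 |
|---|---|---|
| Blinding status after day 60 | Open-label | Allocation undisclosed |
| When the blind ends | Not stated | Database final, after recruitment and last-patient follow-up |
| Who is covered | Not stated | Participant, investigator, research team, committees |
| Procedure for telling participants | None | None at day 60 |

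The conflict is direct. The sections that describe the phase in operation (4.1.3, 4.1.4, 8.3 and 8.5) say nothing about blinding either way, so they do not resolve it.

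**2. Are outcomes collected in the period?** Yes: day 90 FSS as a secondary placebo comparison (synopsis and section 12.11), and day 90/180 FSS and EQ-5D-5L as an objective (synopsis and section 2.2).

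**3. Is the primary outcome touched?** Not at day 60. Those ratings are collected before the period labelled open-label begins.

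**4. How much could it matter?** The documents give no estimate of reporting bias, so the shift *b* below is an assumption. The other inputs come from section 12.3: SD 1.7, 500 per arm, one-sided 0.025. They were set for day 60 and are borrowed here for day 90.

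SE of the difference = 1.7 × √(2/500) = 0.108.

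With no true effect at day 90, the chance of a result favouring the drug at one-sided 0.025 is P(Z > 1.96 − b/SE). For b = 0.10: 0.10/0.1075 = 0.93, then 1.96 − 0.93 = 1.03, giving 15.2%.

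| Assumed shift b (FSS points) | 500 per arm | 450 per arm (10% dropout) |
|---|---|---|
| 0 | 2.5% | 2.5% |
| 0.05 | 6.8% | 6.4% |
| 0.10 | 15.2% | 14.1% |
| 0.15 | 28.6% | 26.2% |
| 0.20 | 46.0% | 42.3% |

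This is a fixed-sample calculation without covariate adjustment. It shows that a large trial is sensitive to a small systematic shift. It does not predict how large the shift would be.

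**The case against.** **The label may be loose wording.** No study drug is given after day 60, so open-label may simply mean off treatment. No code break is described, and section 6.1 is the only operational rule on disclosure. This stands as a limit: the harm follows only if section 4.1 is applied as written. It does not remove the contradiction, and a site could read the label literally. Section 6.1 opens with the aim "To minimize the potential for bias during the treatment phase", and section 11.2 ties adjudication to the blinded treatment phase. Both could suggest that the blind ends at day 60, although the concealment rule in section 6.1 runs well beyond it.

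**The outcomes are of lower rank.** The synopsis (Statistical Methods) bases primary and secondary outcomes on day 60. Section 2.2 has no separate day 90 FSS comparison. Section 12.5 makes all secondary analyses exploratory. Section 12.11 names days 30 and 60 as the key secondary fatigue scores. This lowers the stakes and stands. Even so, day 90 FSS remains a listed secondary comparison with placebo, and calling an analysis exploratory does not remove bias from its estimate.

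**Three stronger readings are not supported.**

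- *That results would be unblinded during ongoing recruitment.* The protocol describes no disclosure at day 60, and section 6.1 forbids it.
- *That disclosure would make later assignments predictable.* Section 12.2 says: "Randomization will be stratified by participating primary care facility with varying block sizes of participants". Block sizes and recruitment rates are not given, and varying block sizes are themselves a safeguard. The result depends entirely on what is assumed: a block of 6 at 4 recruits a month fills in 6/4 = 1.5 months (about 45 days), before its first member reaches day 60, whereas a block of 9 at 2 a month takes 4.5 months.
- *That the primary analysis is compromised, because section 12.5 names day 90 for the primary outcome.* The synopsis, section 2.1, section 12.3 and section 12.11 all give day 60. The day 90 in section 12.5 is a separate inconsistency to correct on its own.

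**Conclusion.** The plan is wrong as written on one point: sections 4.1 and 6.1 give incompatible blinding rules for the day 90/180 period. If section 4.1 governs, the self-reported day 90 FSS comparison and the day 90/180 FSS and EQ-5D-5L durability objective are open to expectation bias. If section 6.1 governs, they are not.

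The size of that bias cannot be taken from the documents. The illustrative range of 6.8% to 46.0% rests on assumed shifts of 0.05 to 0.20 points, no true effect at day 90, and planning values borrowed from day 60. The contradiction is certain; whether any participant would actually be unblinded is not. This is a necessary reconciliation of text with consequences limited to exploratory follow-up results, and it does not threaten the day 60 primary outcome.

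**What to change.** In section 4.1, replace the sentence "This phase is an open-label, post-study phase" with wording to this effect: off-treatment follow-up; participants, site staff and assessors remain blinded until database lock, except for individual unblinding for safety. This agrees with section 6.1, and no other section needs a matching change.

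If open-label follow-up is truly intended, amend section 6.1 instead, state when and by whom each participant is unblinded, and label the day 90 and day 180 comparisons as open-label and exploratory in the synopsis, section 2.2 and section 12.11.

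The first option costs one amended sentence, and participants learn their allocation later. The second costs several edits and the blinded reading of durability.
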